5 CRITERIA FOR EVALUATION

5.1 Primary Endpoint

The primary outcome will be the safety and tolerability of a single infusion of allogeneic hMSCs. Study participants will be monitored for potential dose limiting toxicities. The dose limiting toxicity (DLT) definition consists of the emergence of infusion-related allergic AEs as well as regimen related toxicities. For this study, a DLT will be considered for the occurrence in the first 24 hours after hMSC infusion of a grade ≥ 3 infusion-related allergic toxicities, which include rash, flushing, urticaria, dyspnea, fever $>40^{\circ}\text{C}$ ($>104.0^{\circ}\text{F}$) as scored according to the National Cancer Institute (NCI) Common Terminology Criteria for Adverse Events (CTCAE) version 4.0. Finally, the CTCAE will be used to assess and grade AE severity, including laboratory abnormalities judged to be clinically significant. In addition to infusion related toxicities, special focus will also be placed upon detecting pulmonary exacerbations since anti-inflammatory therapies theoretically could suppress the immune system to the point where it leads to increased infectious complications. Appendix I lists the criteria for defining a pulmonary exacerbation treated with antibiotics. All AEs encountered during the study period will be captured and graded.

In addition to DLT, safety and tolerability of a single infusion of allogeneic mesenchymal stem cells will also be determined by

- Incidence and severity of AEs
- Number of pulmonary exacerbations (modified Fuch's definition⁹⁵)
- Diary reports (Cystic Fibrosis Respiratory Symptom Diary)
- Changes in subject reported symptoms as captured by the Respiratory and Systemic Symptoms Questionnaire from Baseline (Visit 2) Day 1 to Baseline (Visit 2) Day 2, Visits 3, 4, 5, 6, and 7 and at times when a pulmonary exacerbation is being considered.
- Changes in physical examination
- Changes in vital signs including oxygen saturation checked throughout the infusion

- Changes in spirometry (FEV₁ %, FEV₁ (Liters), FEF₂₅₋₇₅) determined 30 minutes, 4 hours and 24 hours after completion of infusion and from Baseline (Visit 2) Day 1 to Baseline (Visit 2) Day 2, Visits 3, 4, 5, 6 and 7.
- Change in sputum quantitative microbiology (change in bacterial colony forming units between Baseline Day 1 and Day 7 and Day 28)
- Changes in hematology, comprehensive chemistry, erythrocyte sedimentation rate (ESR), high-sensitivity C-reactive protein (hs-CRP), and urinalysis results

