8 STUDY TREATMENTS

8.1 Method of Assigning Subjects to Treatment Groups

In this Phase I open-label study, there is no placebo group. All subjects will receive a single infusion of hMSCs. 15 eligible subjects will be recruited from the adult CF Center located at Rainbow Babies and

Children's Hospital and will receive a single dose of one of the following doses of hMSCs: 1×10^6 , 3×10^6 or 5×10^6 hMSCs/kg body weight. A traditional 3+3 design will be utilized (Figure 4). If a maximum tolerated dose (MTD) is identified among the 3 doses, the next 3 subjects enrolled will receive the identified MTD. If there are no DLTs or one DLT, the next 3 subjects enrolled will receive same dose. If there are two or more DLTs, the next lower dose will be used as the MTD for the final 3 enrolled study subjects.

[figure not shown]

Figure 4. Study design for determining dose-limiting toxicity

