8.3.3 Dosage/Dosage Regimen

The first cohort of 3 subjects enrolled will receive a single infusion of 1×10^6 hMSCs/kg body weight. The second cohort of three subjects enrolled will receive a single infusion of 3×10^6 hMSCs/kg, and the third cohort of three subjects enrolled will receive a single infusion of 5×10^6 hMSCs/kg. The first subject in the subsequent cohort will not be enrolled until the last subject in the preceding cohort has completed Visit 5 (Day 28). There will be a minimum of 1 week between the dosing of each study subject in the first three cohorts. The final six subjects will receive a single infusion of 5×10^6 hMSCs/kg if that dose was well tolerated. If the highest dose was not well tolerated, then the final six subjects will receive the maximum tolerated dose (either 1×10^6 or 3×10^6 hMSCs/kg body weight).

Table 1: hMSC dose cohorts

Cohort 1	1×10^6 hMSCs/kg	3 subjects
----------	--------------------------	------------

Cohort 2	3×10^6 hMSCs/kg	3 subjects
Cohort 3	5×10^6 hMSCs/kg	3 subjects
Cohort 4	MTD	6 subjects

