8.4 Supply of Investigational Product at the Site

The cell product will be expanded to the clinical dose in culture upon receipt of a physician investigator's order. Duration of culture expansion is approximately 15-20 days after which cells will be infused once release tests are complete.

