14 DATA SAFETY MONITORING

The Cystic Fibrosis Foundation Data Safety Monitoring Board (DSMB) will establish a Data Monitoring Committee (DMC) to review data relating to safety and efficacy, to conduct and review interim analyses, and to ensure the continued scientific validity and merit of the study, according to the Cystic Fibrosis Foundation Data Safety Monitoring Board Operations Manual and a DMC Charter to be established for this protocol. There will be 3 interim review(s) conducted by the DMC for the purpose of monitoring study conduct and assessing subject safety. Enrollment for subsequent cohorts will not begin until after the DMC reviews the data for the current cohort and approves proceeding to the next cohort. Further details regarding the timing and content of the interim reviews is included in the statistical section below.

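### Section 8.1 steps the last three subjects down a dose after two or more DLTs at the MTD; section 8.3.3 and Table 1 give the final six one dose, with no check after three

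*Combined protocol and SAP*

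**What the plan says.** Section 8.1 adopts a traditional 3+3 over 1, 3 and 5 x 10^6 hMSCs/kg. Once an MTD is identified, three subjects receive it. Then: "If there are no DLTs or one DLT, the next 3 subjects enrolled will receive same dose". Otherwise: "If there are two or more DLTs, the next lower dose will be used as the MTD for the final 3 enrolled study subjects".

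Section 8.3.3 covers the same subjects differently. "The final six subjects will receive a single infusion of" 5 x 10^6/kg, provided that dose was well tolerated. "If the highest dose was not well tolerated, then the final six subjects will receive the maximum tolerated dose", which may be 1 or 3 x 10^6/kg. Table 1 lists cohort 4 as six subjects at the MTD.

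Three other provisions bear on the point:

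- Section 5.1 sets the DLT window: "a DLT will be considered for the occurrence in the first 24 hours after hMSC infusion".
- Section 8.3.3 requires at least a week between subjects, but only in the first three cohorts. Its Visit 5 hold applies between cohorts.
- Section 14: "There will be 3 interim review(s) conducted by the DMC", and "Enrollment for subsequent cohorts will not begin until after the DMC reviews the data for the current cohort" and agrees to proceed.

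**The concern.** A site that doses cohort 4 from section 8.3.3 and Table 1 would find nothing telling it to stop after three subjects. A site that works from section 8.1 would. The two texts give different doses to the last three subjects only when at least two of the previous three have had a grade 3 or higher infusion reaction, which is when the rule is needed. Section 15.3 names determination of the MTD as the primary endpoint, so the rule that can revise the MTD ought to read the same wherever dosing is described.

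There is also a gap inside section 8.1. Section 8.3.3 allows the MTD to be 1 x 10^6/kg. Two or more DLTs at that dose would call for a next lower dose that does not exist, and no stop is stated.

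**Working it through.** **1. The total does not settle it.** Section 8.3.3 gives 3 + 3 + 3 + 6 = 15. Section 8.1 gives 3 + 3 + 3 + 3 + 3 = 15. Both match the planned 15.

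**2. The two rules by outcome.** DLTs are counted among the first three subjects at the identified MTD, which is how the sequence in 8.1 reads, although it does not name the counting set.

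| DLTs in first three of cohort 4 | Last three under 8.1 | Last three under 8.3.3 and Table 1 |
|---|---|---|
| 0 or 1 | same dose | same dose |
| 2 or 3, MTD at 3 or 5 x 10^6/kg | one dose lower | same dose |
| 2 or 3, MTD at 1 x 10^6/kg | not defined | same dose |

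**3. Other safeguards in the text.** Four cohorts have three transitions, which matches the three DMC reviews. Those reviews are tied to moving between cohorts, and none is stated inside cohort 4. The one-week interval does not reach cohort 4. The 24-hour window makes a check after three feasible.

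**4. How often the sections part.** The documents give no DLT rate, so p is an assumption, held equal across doses. A dose passes escalation with 0/3, or with 1/3 followed by 0/3:

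s = (1-p)^3 + 3p(1-p)^2 x (1-p)^3

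An MTD is declared whenever the lowest dose passes, so its probability is s. Two or more DLTs in the next three has probability

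t = 3p^2(1-p) + p^3

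The sections part with probability s x t. The MTD is the lowest dose, and the event occurs there, with probability s(1-s) x t.

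The closest dose-matched evidence in the protocol is section 1.3.4.3.2: no infusion-related toxicity in 43 transplant patients at 1-5 x 10^6/kg. The one-sided 95% upper bound is 1 - 0.05^(1/43) = 6.7%. At p = 0.067, s = 0.8122 + 0.1750 x 0.8122 = 0.954 and t = 0.0129, so s x t = 0.0123.

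| Assumed p | Sections part | Of which at lowest dose |
|---|---|---|
| 1% | 0.03% | under 0.001% |
| 2% | 0.12% | under 0.001% |
| 5% | 0.7% | 0.02% |
| 6.7% | 1.2% | 0.06% |
| 10% | 2.5% | 0.24% |
| 20% | 7.4% | 2.1% |

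**5. What is known about the dose when it happens.** If the dose passed on 0/3, the record is at least 2/6 (Clopper-Pearson 95% interval 4% to 78%). If it passed on 1/6, the record is at least 3/9 (7% to 70%). Either way the observed rate is 33% or more. For three further subjects at that dose, the chance of at least one more DLT is 1 - (1-p)^3: 49%, 70% and 88% if the true rate is 20%, 33% or 50%. These figures describe the consequence, not the frequency.

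**The case against.** The best reply is that section 8.1 is the section on assigning subjects to dose, its rule is explicit, and section 8.3.3 merely summarizes the regimen. Section 8.3.3 makes the top dose conditional on tolerability, and 8.1 calls the lower dose the MTD, so Table 1's label could fit either outcome. Much of this stands. A reader might infer that 8.3.3 directs continued dosing after two DLTs. The documents do not support that: 8.3.3 leaves the 8.1 rule out and does not expressly override it. What remains is that no order of precedence is stated, that one dose for all six cannot be squared with a 3 + 3 split, and that 8.1 has no answer at the lowest dose under any reading.

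A reader might also infer that nobody is assigned to review the DLT count. That is not secure. The synopsis names a medical monitoring group and a DMC, and the contents list a section 11.3 on medical monitoring that was not available. Figure 4 and the DMC charter were not available either. Any of these may supply a check, though the wording of 8.1 and 8.3.3 would still differ.

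The event is also rare, and that objection stands in full. The probability t taken alone runs from 2.8% to 50% for rates of 10% to 50%, which could make the trigger look common. Those are high assumed rates, and t omits the chance that any dose passes. At 50%, s = 0.125 + 0.375 x 0.125 = 0.172, so the joint chance is 0.172 x 0.5 = 8.6%.

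**Conclusion.** The point holds as a textual conflict with a safety consequence, and it should be fixed. Sections 8.1 and 8.3.3 prescribe different doses for the last three subjects after two or more DLTs in the first three at the MTD, and 8.1 is undefined if this happens at 1 x 10^6/kg. For assumed rates up to the 6.7% benchmark the chance is 0.03% to 1.2%. The case for acting rests on severity and low cost, not on frequency.

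The probabilities assume independent subjects, an equal DLT rate at all doses, and a traditional 3+3. The benchmark comes from a different population that received cells from MHC-identical donors, so it is only a guide. If 8.1 meant DLTs to be pooled with earlier subjects at the same dose, the trigger after 0/3 is unchanged, and after 1/6 a single further DLT would suffice. The conflict remains in both cases.

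A reader might go on to infer that a 3+3 with six further subjects cannot be held to 15. The text shown does not settle this, because Figure 4 may say how expansion subjects are counted. It is a query, not a finding.

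**What to change.** Amend section 8.3.3 to repeat the 8.1 rule, and show cohort 4 in Table 1 as 3 + 3:

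- Treat three subjects at the MTD. Do not dose the fourth until the third has completed the 24-hour DLT window and the DLT count has been confirmed, for example by the existing medical monitor.
- After 0 or 1 DLT among these three, the last three receive the same dose.
- After two or more, they receive the next lower dose.
- After two or more at 1 x 10^6/kg, stop dosing. Add this to section 8.1 as well.

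If Figure 4, section 11.3 or the DMC charter already contains any of this, a cross-reference from 8.3.3 is enough for that part. Ask separately whether Figure 4 counts 3+3 expansion subjects within the 15.

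The cost is wording and a pause of about a day. Cell supply needs some planning: "Duration of culture expansion is approximately 15-20 days after which cells will be infused once release tests are complete". The fourth infusion should therefore be scheduled at least a day after the third. A step-down needs fewer cells than were already ordered. The planned 15 does not change.

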8.2 Blinding

Because this is an open-label, safety and tolerability study in which all enrolled subjects will receive hMSCs, this study is unblinded.

8.3 Test and Control Formulation

The biological product (hMSCs) is manufactured in the Case Western Reserve University NCRM Cellular Therapy Laboratory under GMP-compliant regulations. This laboratory is located on the campus of Case Western Reserve University/University Hospitals Cleveland Medical Center.

Address:
 [name]
 [name]
 [name]
 [contact]

The cells obtained from the donor(s) will be cryopreserved at primary culture. There will be no passages involved. Only plated and adherent cells will be harvested. This occurs at approximately 14 days. The number of passages after thaw (prior to infusion) is dependent on the target dose (recipient receives a dose based upon weight). For most participants, we will likely reach our target dose after 2 passages and no greater than 3 passages. This translates into approximately 14 days.

The final hMSC formulation is a fresh cell suspension of 4×10^6 cells/ml with $\geq 70\%$ viability in Plasma-Lyte A + 2.5% HSA. This product is distributed in a syringe for immediate infusion.

8.3.1 Packaging and Labeling

The biologic product is packaged and labeled for infusion according to FDA guidelines by Cell Processing Technologists employed by the CWRU NCRM Cellular Therapy Lab. Blinding is not applicable to this study. The infusion product will be labeled as follows:

Investigational Drug (Study Name or #)

FOR INFUSION

Subject Unique Identifier:

Cellular Therapy Laboratory

[name]

[name]

[name] [contact]

Date:

Total Cells:

Volume: X ml

Expiration: dd/mm/yyyy Time hh:mm

CAUTION: NEW DRUG-LIMITED BY FEDERAL LAW TO INVESTIGATIONAL USE

8.3.2 Handling/Dispensing

Human MSCs will be dispensed directly from manufacturing personnel to clinical personnel per conditions noted in the IND application and the clinical protocol. Chain of custody will be tracked in writing and documents filed in both the subject study record and manufacturing record.

8.3.3 Dosage/Dosage Regimen

The first cohort of 3 subjects enrolled will receive a single infusion of 1×10^6 hMSCs/kg body weight. The second cohort of three subjects enrolled will receive a single infusion of 3×10^6 hMSCs/kg, and the third cohort of three subjects enrolled will receive a single infusion of 5×10^6 hMSCs/kg. The first subject in the subsequent cohort will not be enrolled until the last subject in the preceding cohort has completed Visit 5 (Day 28). There will be a minimum of 1 week between the dosing of each study subject in the first three cohorts. The final six subjects will receive a single infusion of 5×10^6 hMSCs/kg if that dose was well tolerated. If the highest dose was not well tolerated, then the final six subjects will receive the maximum tolerated dose (either 1×10^6 or 3×10^6 hMSCs/kg body weight).

Table 1: hMSC dose cohorts

Cohort 1	1×10^6 hMSCs/kg	3 subjects
----------	--------------------------	------------

Cohort 2	3×10^6 hMSCs/kg	3 subjects
Cohort 3	5×10^6 hMSCs/kg	3 subjects
Cohort 4	MTD	6 subjects

8.3.4 Administration Instructions

The person infusing the cells should wear sterile gloves.

Fresh hMSC will be administered as follows:

hMSCs are infused through a peripheral venous catheter by directly connecting the syringe of cells to the IV tubing via Y-connector.

1. Start infusing IV fluids (normal saline) at the maximal rate (250 ml/hr.).
2. Clean the port of the Y-connector as per hospital protocol.
3. Remove needle from syringe containing the hMSCs.
4. Attach the syringe with hMSCs directly to the in-line Y-connector.
5. Manually clamp the IV tubing leading back to the bag of saline behind the syringe by pinching the tubing between two fingers.
6. Administer a small aliquot (2-3 ml) of the cells from the syringe by slow IV push.
7. Release the IV tubing and allow the normal saline to flush the line for 1-2 minutes.
8. Repeat steps 5 through 7 until all the cells have been infused, completing the infusion over 10-15 minutes.
9. The first post cell infusion rinse of the syringe must now be performed.
10. Manually clamp the IV tubing between the syringe and the study participant by bending the tubing and pinching it between two fingers to draw saline fluid into the syringe, complete filling the syringe.
11. Release the IV tubing leading between the syringe and the study participant.
12. Manually clamp the IV tubing between the bag of saline and the syringe by bending the tubing and pinching it between two fingers.
13. Administer an aliquot (3-5 ml) of fluid from the syringe by IV push.
14. Release the IV tubing and allow the normal saline to flush the line for 30 seconds to 1 minute.
15. Repeat steps 12 through 14 until the syringe is empty. Completing the saline rinse should take approximately 2 minutes.
16. Perform a second post cell infusion rinse of the syringe.
17. Repeat steps 10 through 15.
18. Remove the syringe from the Y-connector port.

19. Administer normal saline through the running IV at a rate of 250 ml/hr. for 4 hours while the study participant is being monitored after the infusion.
20. Document the infusion in a procedure note in the electronic medical record (EMR).

Infusion reactions are documented in the subject's study chart and the principal investigator is notified in the event of severe reactions.

An infusion side-effect checklist is provided to the subject's nurse (a modified version of the standard form used by University Hospitals Cleveland Medical Center Seidman Cancer Center).

Side effects are monitored for 24 hours after the completion of the infusion.

8.4 Supply of Investigational Product at the Site

The cell product will be expanded to the clinical dose in culture upon receipt of a physician investigator's order. Duration of culture expansion is approximately 15-20 days after which cells will be infused once release tests are complete.

8.4.1 Storage

Stock vials of primary culture hMSCs will be secured in liquid nitrogen vapor phase until indicated for expansion per physician investigator's order. Liquid nitrogen freezers are remote alarm monitored 24/7. The expanded hMSCs for infusion will be used fresh without further frozen storage.

8.5 Investigational Product Accountability

An accurate and current accounting of the amount of hMSCs administered to each subject will be maintained by research staff. Research staff will document the total dosage of hMSCs administered to each subject. If the infusion is stopped for any reason, including adverse reaction or technical difficulty, research staff will determine how much of the infusion the subject received and record the administered dose in the study records.

8.6 Measures of Treatment Compliance

In this Phase I study, subjects will receive a single infusion of hMSCs that will be administered by research staff in the Dahms Clinical Research Unit of University Hospitals Cleveland Medical Center. Therefore we do not anticipate that there will be any issues with treatment compliance during this study.

9 STUDY PROCEDURES AND GUIDELINES

A Schedule of Events representing the required testing procedures to be performed for the duration of the study is outlined in Appendix II.

Prior to conducting any study-related activities, written informed consent and the Health Insurance Portability and Accountability Act (HIPAA) authorization must be signed and dated by the subject.

9.1 Clinical Assessments

9.1.1 Concomitant Medications

All concomitant medications and concurrent therapies will be documented at all study visits including an Acute Illness/Early Termination Visit when applicable. Dose, route, unit frequency of administration, and indication for administration and dates of medication will be captured for the 30 days prior to screening.

9.1.2 Demographics

Demographic information (date of birth, gender, race) will be recorded at Screening.

9.1.3 Medical History

Relevant medical history, including history of current disease, *cftr* genotype analysis results, sweat chloride results, sputum microbiology, spirometry results, other pertinent respiratory history, and information regarding underlying diseases will be recorded at the screening visit (Visit 1). An interval history will be obtained at all other visits.

In the event of a pregnancy between Visit 2 (Day 1) and Telephone Call 3 (Day 56), medical information pertaining to the pregnancy will be collected through the birth of the child or the termination of the pregnancy.

9.1.4 Physical Examination

A complete physical examination will be performed by a physician (either the investigator or a sub-investigator) at Visits 1, 2 and 5 and at an Acute Illness/Early Termination Visit. Qualified staff (MD/DO, NP, RN, PA) may complete the abbreviated physical exam at all other visits. The physical exam also includes height (at screening only) and weight. The complete physical examination consists of general, HEENT, neck/thyroid, lymph nodes, cardiovascular system, chest/lung, abdomen, extremities, skin, musculoskeletal, nervous system, mental status, and other. An abbreviated exam will consist of HEENT, cardiovascular system, chest/lung, abdomen, extremities, skin, and other. New abnormal physical exam findings must be documented and will be followed by a physician or other qualified staff at the next scheduled visit.

9.1.5 Vital Signs

Body temperature, blood pressure, pulse and respirations will be performed after resting for 5 minutes at all study visits.

9.1.6 Oximetry

Oximetry will be measured on room air with the subject at rest at all study visits.

9.1.7 Spirometry

Spirometry will be performed at all study visits and in accordance with the current American Thoracic Society recommendations for the performance and interpretation of tests. Spirometry will be obtained approximately 2 hours prior to the start of the hMSC infusion and 30 minutes, 4 hours and 24 hours after completion of the infusion. Subjects will perform spirometry as is customary for that subject at clinical visits. If the subject typically does not take albuterol prior to spirometry, then he/she will not take albuterol prior to spirometry during the study. If the subject typically takes albuterol prior to spirometry, they he/she will take albuterol prior to spirometry for this study. However there is an exception. In any subject in which it is anticipated that he/she might not be able to produce sputum spontaneously at any one of the study visits in which sputum will be obtained, then those subjects will undergo sputum induction at all visits regardless of his or her ability to spontaneously expectorate sputum at the current study visit. In these cases, those individuals will receive three inhalations of albuterol sulfate via metered dose inhaler prior to all spirometric tests obtained during the study. Approximately 15 minutes after administering albuterol sulfate, pulmonary function testing will be performed. If a study subject is unable to produce sputum at the Baseline Visit (Day 1), then sputum will not be obtained at Visits 3 (Day 7) and 5 (Day 28).

